#### 6.6.1.1. VOD

Summaries focused on VOD/SOS (The MedDRA PTs of Venoocclusive liver disease and Venoocclusive disease) will include the following number and percentage of patients out of the following groups (denominator):

- Any VOD with denominator of safety analysis set
- VOD before (first) follow-up HSCT with denominator of safety analysis set
- VOD before (first) follow-up HSCT with denominator of safety analysis set with a prior HSCT
- VOD after follow-up HSCT with denominator of safety analysis set with a follow-up HSCT
- VOD after follow-up HSCT with denominator of safety analysis set with both a prior and a follow-up HSCT.

Timing relative to study treatment and HSCT (days): The timing of the first VOD relative to the nearest prior GO dose will be summarized with descriptive statistics (VOD start date – nearest GO dose date +1). The timing of the first HSCT relative to the nearest VOD after the

HSCT date (days) will be summarized with descriptive statistics (VOD start date – first HSCT date +1).

#### **6.6.1.2. Basic Results**

The following additional summaries required for basic results disclosures in the US and EU will be provided:

- Treatment Emergent Non Serious Adverse Events by SOC and PT (All Causality) in >5% of patients in either group;
- Treatment Emergent Non Serious Adverse Events by SOC and PT (All Causality);
- Treatment Emergent Serious Adverse Events by SOC and PT; and
- Fatal Adverse Events by SOC and PT (based on safety database).

Each of the above summaries for EU will include a count of the number of occurrences of all causality events and the number of occurrences of treatment related events.

#### **6.6.2. Deaths**

The frequency (number and percentage) of patients in the safety analysis set who died and who died within 36 days after last dose of study treatment as well as the cause of death, will be tabulated based on information from the 'Notice of Death' CRFs.

The frequency (number and percentage) of patients in the safety analysis set who died within 30 days of first dose of study treatment will also be provided.

Date and cause of death will be provided in individual patient data listing (as needed to be compliant with ICH required listings) together with selected GO dosing information (date of first / last administration).

Refer to Section 6.2.4 for the description of the summaries of all deaths observed in the study.

#### **6.6.3. Laboratory Data**

Laboratory results will be converted to International System of Units (Système International d'unités, SI) units which will be used for applying toxicity grades and for all summaries.

Laboratory data will be graded programmatically according to the NCI CTCAE v4.03 severity grade (including low and high values if both are defined for the parameter). Non-numeric qualifiers will not be taken into consideration in the derivation of grade (e.g. hypokalemia Grade 1 and Grade 2 are only distinguished by a non-numerical qualifier and therefore Grade 2 will not be derived). In summaries the number and percentage of patients corresponding to grades that only include non-quantitative criteria will be displayed as a

blank or NA (not assessed). If there is any overlap between grade criteria (e.g. CTCAE grading criteria for Creatinine Increased – a value can fall into one range based on comparison to ULN and another range based on comparison to baseline), the highest (worst) grade would be assigned to that record. Grade 5 is defined in the CTCAE criteria guidance as an event with an outcome of death. Since laboratory data does not collect an outcome, Grade 5 is not used when programmatically grading laboratory data.

Grade 0 or Outside Toxicity Reference (OTR) is not defined specifically by in the CTCAE guidance. However, programmatically this is used as a category to represent those patients who did not meet any of the Grades 1 to 4 criteria. If the laboratory value is evaluable for CTCAE criteria grading (numeric value is present, valid units and ranges are present as required to allow conversion to standard units and grading), and does not qualify for any of the Grade 1-4 criteria for a given laboratory test, then the value is assigned as Grade 0 or OTR.

For **WBC differential counts** (total neutrophil [including bands], lymphocyte counts), the absolute value will be used when the results are reported in this manner. When only percentages are available the absolute value will be derived as follows:

$$\text{Derived differential absolute count} = (\text{WBC count}) \times (\text{Differential \%value} / 100)$$

If both the absolute and % value for Neutrophils or Lymphocytes are reported from the same laboratory sample date and patient, ONLY the absolute value will be graded. The % value will not be graded in this scenario. Further details of the grading of the computed absolute values are provided in Section 5.3.3.

Several laboratory tests have bi-directional grading criteria defined so that both low (hypo) and high (hyper) values will be graded separately. Each criterion will be summarized separately. In the cases where a value is graded as a Grade 1, 2, 3, or 4 for one of the directions, that value will also be assigned as a Grade 0 for the opposite direction for that test. For example, a value meeting the criteria for Grade 3 Hypercalcemia will be classified as a Grade 0 Hypocalcemia.

The following summaries will be provided for the safety analysis set.

The denominator for percentages will be the number of patients treated in the group being summarized with at least 1 post baseline assessment of the laboratory parameter.

Displays will be organized by laboratory category: Hematology parameters including coagulation parameters will be summarized together, chemistry parameters will be summarized together, and urinalysis parameters will be summarized together. Laboratory parameters with CTCAE grades will be summarized separately from laboratory parameters with no CTCAE grades.

For each CTCAE term, patients will be counted according to the worst (maximum) CTCAE grade on treatment (excluding baseline values). Baseline is defined in Section 3.4. If there are multiple assessments that meet the baseline definition on the same day without the ability

to determine which was truly last, then the worst CTC grade will be assigned as the baseline CTC grade.

The following summary tables will be created:

- Shift summary of laboratory parameters of baseline CTCAE grade by maximum post baseline CTCAE grade.
- Shift summary of laboratory parameters from  $\leq$  Grade 2 at baseline to  $\geq$  Grade 3 post-baseline.

The non-CTC graded laboratory tests (red blood cells, hematocrit, BUN, LDH) along with urinalysis test (pH) will be presented according to the following categories overall: below normal limit, within normal limits, and above normal limits. In the unlikely event that for a given participant, clinically significant abnormalities are noted in both directions (eg,  $>$  ULN and  $<$  LLN), then both abnormalities are counted. The remaining urinalysis tests (albumin, glucose, blood/hemoglobin, ketones/acetone) will be categorized as negative or positive.

A shift summary of laboratory test results with no CTCAE criteria of baseline assessment by worst on-treatment assessment will be created. .

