4.1. Inclusion Criteria

Patients must meet all of the following inclusion criteria to be eligible for enrollment into the study:

1. Refractory or relapsed (ie, bone marrow blasts $\geq 5\%$) CD33-positive AML.
2. Age ≥ 12 years.
3. Eastern Cooperative Oncology Group (ECOG) Performance Status 0 to 2.
4. Initial peripheral white blood cells (WBC) counts $< 30,000/\mu\text{L}$; patients with a higher WBC count should undergo cytoreduction.
5. Adequate renal/hepatic functions, ie:
 - Serum creatinine $\leq 1.5 \times$ upper limit of normal (ULN) or any serum creatinine level associated with a measured or calculated creatinine clearance of $\geq 40 \text{ mL/min}$;
 - Aspartate aminotransferase (AST) and alanine aminotransferase (ALT) $< 2.5 \times \text{ULN}$; total bilirubin $< 2 \times \text{ULN}$.
6. Negative serum or urine pregnancy (human chorionic gonadotropin [hCG]) test within 1 week before treatment for women of child bearing potential.
7. Evidence of a personally signed and dated informed consent document and obtaining proper pediatric assent in addition to consent according to local regulations (by the caregivers or legally acceptable representative [eg, parents] in the pediatric patients) indicating that the patient [or a legally acceptable representative/parent(s)/legal guardian] has been informed of all pertinent aspects of the study.
8. Willing and able to comply with scheduled visits, treatment plan, laboratory tests, and other study procedures.

9. Female patients of non-childbearing potential must meet at least 1 of the following criteria:
 - Achieved postmenopausal status, defined as follows: cessation of regular menses for at least 12 consecutive months with no alternative pathological or physiological cause; status may be confirmed with a serum follicle-stimulating hormone (FSH) level confirming the postmenopausal state;
 - Have undergone a documented hysterectomy and/or bilateral oophorectomy;
 - Have medically confirmed ovarian failure.

All other female patients (including female patients with tubal ligations) are considered to be of childbearing potential.

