### 3.4. Baseline Variables

ECG parameters: The last available planned triplicate measurements prior to first dose according to the date (selected from nominal time points of Screening and Cycle 1 Day 1 at 0 hours) will be used as baseline. Triplicate ECGs are collected; therefore the baseline for each ECG measurement is the average of the pre-dose measurements on the selected baseline day. Refer to Section 5.2.8 for further details of derivations concerning ECG parameters.

For safety (including Eastern Cooperative Oncology Group (ECOG) performance status, safety laboratory results, blasts in the bone marrow, blasts in the peripheral blood, immunogenicity) the last assessment performed on or prior to date of the first dose of study treatment will be designated as the baseline assessment. If there are no observations meeting these criteria, then baseline is considered missing. For laboratory data, if there are multiple assessments that meet the baseline definition on the same day without the ability to determine which was truly last, then the worst CTC grade will be considered as the baseline grade.

CD33 expression: CCI (percent positivity CCI [REDACTED] the baseline value will be based on the bone marrow sample that is the last available assessment on or prior to the date of first dose of study treatment. If there is no result available from bone marrow, then a result from a blood sample meeting the same criteria will be used. CCI [REDACTED]

Additionally, percent positivity will be categorized as < 30, 30 - <70,  $\geq$  70; CCI [REDACTED]

The date of first dose (start date) of study treatment is the earliest date of GO dosing.

The date of last dose of study treatment is the latest date of GO dosing.

No windowing will be applied when defining baseline. Although the protocol requires screening assessments to be performed within 28 days prior to first dose; values outside this window will not be excluded when determining baseline assessments.

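### The percentage in the SAP's Grade ≤2 to Grade ≥3 laboratory shift table is not an incidence among patients at risk, because its denominator includes patients who cannot shift

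*SAP*

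**What the plan says.** SAP 6.6.3 introduces its laboratory tables with "The following summaries will be provided for the safety analysis set" and then states a single rule, under which each percentage is taken over "the number of patients treated in the group being summarized with at least 1 post baseline assessment of the laboratory parameter". The rule refers to treatment and to a post-baseline value. It does not mention the baseline grade.

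Two tables of CTCAE grades follow:

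- "Shift summary of laboratory parameters of baseline CTCAE grade by maximum post baseline CTCAE grade", which is the full cross-tabulation;
- "Shift summary of laboratory parameters from" Grade 2 or lower at baseline to Grade 3 or higher after baseline, which is the table at issue here.

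Neither has a denominator of its own. Post-baseline status is the worst on-treatment grade, with baseline values left out. For baseline, SAP 3.4 says that "the last assessment performed on or prior to date of the first dose of study treatment will be designated as the baseline assessment", and that baseline is missing if no value qualifies.

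On eligibility, Protocol 4.1 opens one criterion with "Adequate renal/hepatic functions, ie" and lists limits for creatinine, AST, ALT and bilirubin. It also caps the white cell count from above. Neither Protocol 4.1 nor the exclusion criteria in 4.2 set a minimum neutrophil, platelet or hemoglobin value.

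**The concern.** A table that starts from patients at Grade ≤2 and counts those who reach Grade ≥3 will usually be read as showing how often a patient without a severe abnormality develops one on treatment. That reading needs a denominator of patients who could make the move. Under the stated rule, a patient who enters at Grade 3 or 4 adds to the denominator and can never add to the numerator. The same is true of a patient with a post-baseline value but no baseline grade.

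The effect runs in one direction, towards a lower percentage, and it differs by row. Patients with relapsed or refractory AML may enter with low counts, and nothing in the eligibility criteria keeps out those with severe cytopenia. The hematology rows are therefore the ones most open to dilution. The hepatic and renal rows are restricted at entry and should be less exposed. Two rows with the same at-risk incidence could then print different percentages.

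Myelosuppression is an adverse event of special interest (SAP 3.5.1.1). SAP version 2 also replaced the worst-grade laboratory summaries with shift tables, partly to supply in-text tables for the study report (SAP section 1, Table 1). The percentage may therefore be read and quoted.

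**Working it through.** The plan states no figure for this table, so there is nothing to reproduce. The check is whether the denominator rule matches the numerator, and what follows if it does not.

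**Inputs.**

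- N: treated patients in the column with at least one post-baseline value of the parameter (SAP 6.6.3). For illustration N = 50, the planned number of adults (SAP 5.1).
- k: those among the N who are at Grade ≥3 at baseline or have no baseline grade. The documents do not give it.
- x: patients with baseline Grade ≤2 and worst post-baseline Grade ≥3.
- p = k/N, and r = x/(N − k), the incidence among patients at risk. Both are assumptions below, shown over a range.

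**Step 1: which patients the rule keeps.** The sentence precedes both tables. In SAP 5.2 the columns are adult, pediatric and total, and SAP 6.6.1 uses the same phrase about the group being summarized for the adverse event denominators. The group is therefore an age column, not a baseline-grade stratum. SAP 5.2.12 adds that missing observations stay in denominators unless something else is specified. So the k patients remain in N.

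**Step 2: the formula.** The printed percentage is x/N. Since x = r × (N − k), x/N = r × (N − k)/N = r × (1 − p). Even if every patient at risk worsens (r = 1), the table cannot print more than 1 − p.

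**Step 3: the size over a range.**

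| p (assumed) | r = 30% | r = 60% | r = 90% |
|---|---|---|---|
| 0 | 30% | 60% | 90% |
| 0.1 | 27% | 54% | 81% |
| 0.3 | 21% | 42% | 63% |
| 0.5 | 15% | 30% | 45% |

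In whole patients, with N = 50 and p = 0.4, 20 patients start severe or ungraded and 30 are at risk. If 18 of the 30 shift, the SAP rule prints 18/50 = 36%, while the at-risk percentage is 18/30 = 60%.

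**Step 4: can p exceed zero?** For neutrophils, platelets and hemoglobin, nothing in Protocol 4.1 or 4.2 prevents it. The footnote to Protocol Table 3 recognises that low neutrophils and platelets may come from the leukemia itself, but it concerns Cycle 2 dosing and gives no baseline frequencies. The missing-baseline part of p should be small. Blood counts and chemistry are scheduled at screening and on Cycle 1 Day 1, results must be checked before dosing (Protocol 6.2.2.1), and SAP 3.4 applies no window when choosing the baseline.

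**Step 5: can a reader undo the dilution?** Yes, from the full cross-tabulation. The baseline Grade 0 to 2 rows sum to N − k, and the cells of those rows at post-baseline Grade 3 or 4 sum to x. Dividing the second by the first gives r. In the whole-patient example this returns 18/30.

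**Step 6: the SAP's practice elsewhere.** Other percentages have denominators fitted to the question. VOD after a follow-up transplant is divided by patients who had one (6.6.1.1). Prolonged cytopenia leaves out patients whose Day 42 status cannot be determined (6.6.3.1). Response by cycle uses only patients who received that cycle (6.2.3). The Grade ≤2 to ≥3 table has no such adjustment.

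**The case against.** The strongest reply is that the percentage is correct for what it literally is: the share of treated, evaluable patients with a new Grade ≥3 value. The SAP nowhere says that the table estimates a risk among patients at risk, and the stated reason for the shift tables is reporting convention. The count x is right under either denominator, and the full table in the same section supplies the rest. All of this stands, and it is why the point is minor. It does not remove the mismatch. The table restricts its numerator by baseline grade and leaves the denominator unrestricted, so the printed number invites a reading that it does not support.

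A reader might infer that the plan hides severe cytopenia, so that sicker patients make the drug look safer overall. The documents do not support that. The dilution affects one percentage in one descriptive table. Severe post-baseline grades appear in full in the other shift table. Myelosuppression is summarized by maximum grade as an event of special interest (SAP 6.6.1), and transfusion days are reported (6.5.4). For responders, so are recovery times and prolonged cytopenia (6.6.3.1).

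A reader might also infer that many patients will start at Grade 3 or 4, or that parameters and age columns can no longer be compared. No baseline counts are given, so the first is inference. On the second, the SAP plans no formal comparison of laboratory shifts between parameters or cohorts, the pediatric cohort has 6 patients, and the full table allows an adjusted reading.

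**Conclusion.** The point holds as a minor reporting correction. Under SAP 6.6.3 as written, the Grade ≤2 to Grade ≥3 percentage equals the at-risk incidence times (1 − p). The direction is certain whenever p is above zero; the size is unknown. The 63% and 45% printed for an at-risk incidence of 90% rest on assumed values of both p and r, and they illustrate the formula rather than predict the results. If no patient in a row is at Grade ≥3 or ungraded at baseline, nothing changes in that row.

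It would go too far to say that the plan understates new severe cytopenia by a known or large amount. The percentage is low only relative to incidence among patients at risk, and that incidence can be recovered from the companion table. The table carries no test or decision rule, and the primary QTc conclusion does not depend on it.

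**What to change.** Add one sentence to SAP 6.6.3, for the Grade ≤2 to Grade ≥3 table only: the denominator is treated patients with a baseline grade of 2 or lower for that parameter and at least one post-baseline value. Print that n in each row, with the number already at Grade ≥3 and the number without a baseline grade beside it. Keep the present denominator for the full baseline-by-worst-grade table, where it fits.

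The cost is that sentence and a row-specific denominator in one table program. No new data are needed. The percentages will be less favourable wherever p is above zero and at least one patient shifts. The denominator will vary from row to row, which the printed n makes visible.

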#### 6.6.3.1. Time To Recovery

The analysis of Time to Recovery of Neutrophils and the analysis of Time to Recovery of Platelets will be similar, therefore this section is written generically as “Time to Recovery”.

Time to Recovery for responders will be reported in days and derived as ((recovery date or censoring date) – date of first dose +1) for each cycle (for responders in that cycle).

The summary will include the number of patients recovered to the level of interest and the number of patients not recovered and reported for the safety analysis set.

Time to Recovery will be summarized using the Kaplan-Meier method. The quartiles will be estimated by the Kaplan-Meier method. Confidence intervals (95%) for quartiles will be based on the Brookmeyer-Crowley method.

The estimated survival curves will be displayed graphically (unless there are  $<$  5 responders) with one graph including estimates for the adult and pediatric patients separately. Graphs will describe the number of patients at risk over time.

**Prolonged Cytopenias (Neutrophils and Platelets):** For each cycle, patients with Time to Recovery longer than 42 days will be considered prolonged and summarized for the safety analysis set. The percentage will be based on a denominator that will exclude patients without data to determine the status at Day 42 relative to the cycle start. Thus prolonged cytopenias applies only to patient who are responders in the respective cycle.

